Psychiatric

CONFIDENTIAL

This material is the property of the University of Pennsylvania. Do not disclose or use except as authorized in writing by the study sponsor

1. Current diagnosis of major depression. Subjects with a history of major depression, in remission for 6 months or longer (may be stable on antidepressant medications), are eligible.
2. Lifetime history of a suicide attempt.
3. Lifetime history of schizophrenia, psychosis, and/or bipolar disorder.

Medication

Current use or recent discontinuation (within the last 14 days) of:

1. Smoking cessation medication (e.g., Zyban, Wellbutrin, Wellbutrin SR, Chantix).
2. Anti-psychotic medications.
3. Prescription stimulants (e.g., Provigil, Ritalin, Adderall).
4. Systemic steroids.

Current use of:

5. Nicotine replacement therapy (NRT).
6. Heart medications such as digoxin, quinidine, and nitroglycerin.

Daily use of:

7. Benzodiazepines and/or Barbiturates.
8. Opiate-containing medications for chronic pain.
9. Inhaled corticosteroids.

Subjects will be instructed to refrain from using any study prohibited drugs/medications (both recreational and prescription) throughout their participation in the study. After final eligibility is confirmed, subjects who report taking contraindicated medication(s) over the course of the study period may only remain eligible if the Study Physician and Principal Investigator determine that the contraindicated medication(s) do/did not significantly impact the study design, data quality, and/or subject safety and welfare. Subjects are permitted to take necessary prescription medications not included within the exclusion list during the study.

General Exclusion

1. Past, current, anticipated, or pending enrollment in another research program over the study period that could potentially impact subject safety, study data, and/or the study design as determined by the Principal Investigator and/or Study Physician.
2. Any medical condition, illness, disorder, adverse event (AE), or concomitant medication that could compromise participant safety or significantly impact study performance as determined by the Principal Investigator and/or Study Physician. Subjects may be deemed ineligible for any of the aforementioned reasons at any point throughout the study, as well as during the initial telephone screen.

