6.2.4 Pre-Quit Visit (~Week -1)

During the Pre-Quit Visit (Duration: ~2 hours) participants will:

1. Perform a CO breath assessment, answer combustible marijuana items, and complete a concomitant medication review.
2. Provide daily smoking rate (timeline follow back [TLFB]).
3. Have weight measured.
4. Participants who required multiple blood pressure readings during the Intake Visit will complete an additional blood pressure reading to reconfirm eligibility to receive TN as scheduled (See Blood Pressure Procedures under Screening/Covariates).
5. Complete paper and pencil questionnaires:
 - Side Effect Checklist (SEC)
 - Adverse Events Form (Open-Ended AEs)
 - Withdrawal Symptoms (MNWS)
 - Smoking Urges/Craving (QSU-B)
 - Positive & Negative Affect (PANAS)
 - Physical Activity (PAR)
6. Complete Session 2 of assigned counseling protocol (BAS+ or SC) and receive TN per a standardized distribution schedule (see section 6.5.1: Treatment; Transdermal Nicotine).

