- A participant presents with a SBP reading greater than 190 mmHg and/or DBP greater than 110 mmHg, s/he will be deemed INELIGIBLE for the study and instructed to seek immediate medical attention (e.g. Emergency Room or Walk-in Clinic).

After the first or second blood pressure reading, if a participant presents with a SBP between 151-159 mmHg and/or DBP between 91-99 mmHg, the research staff will inform the participant that they may have mild, Stage I, hypertension and advise they consult with a physician. The participant will remain ELIGIBLE for the study.

Pre-Quit Visit. Participants who required a second blood pressure at the Intake Visit (i.e. the first measurement was a SBP greater than 159 mmHg and/or a DBP greater than 99 mmHg) will have their blood pressure reassessed at Pre-Quit. If a participant presents with elevated blood pressure (SBP greater than 159 mmHg and/or DBP greater than 99 mmHg), staff will take an additional blood pressure reading after a 10-minute rest period in which the participant will be instructed to sit comfortably. If, after the second reading:

- A participant presents with a SBP reading less than 160 mmHg and a DBP less than 100 mmHg, s/he will be ELIGIBLE to receive TN patches as scheduled.
- A participant presents with a SBP greater than 159 mmHg and/or DBP greater than 99 mmHg, the participant will be required to obtain written permission (a formal letter will be provided by the study team) from their physician in order to receive TN patches. If TN patches are not distributed at the Pre-Quit Visit for this reason, the participant may still participate in the study and receive counseling only. The participant may receive TN patches after the receipt of an approved letter signed by the participant's physician.
- A participant presents with a SBP greater than 190 mmHg and/or DBP greater than 110 mmHg, s/he will be instructed to seek immediate medical attention (e.g. Emergency Room or Walk-in Clinic). The participant may still participate in the study and continue and receive counseling, but they will not have the option to receive TN patches.

After the first or second blood pressure reading, if a participant presents with a SBP between 151-159 mmHg and/or DBP between 91-99 mmHg, the research staff will inform the participant that they may have mild, Stage I, hypertension and advise they consult with a physician. The participant will remain eligible for the study and receive TN patches as scheduled.

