Missed Pre-Quit Visit. For participants requiring a second blood pressure at the Intake Visit (i.e. first measurement was SBP greater than 159 mmHg and/or DBP greater than 99 mmHg) who miss their scheduled Pre-Quit Visit, a blood pressure measurement will occur at the next in-person visit the participant attends. Blood pressure will be collected in accordance with the procedures (Pre-Quit Visit) listed above. TN patches will not be distributed until the participant presents a blood pressure reading within the established eligibility range (post Intake).

CONFIDENTIAL

This material is the property of the University of Pennsylvania. Do not disclose or use except as authorized in writing by the study sponsor

Hypotension: If a participant presents with a SBP less than 90 mmHg at either the Intake Visit or Pre-Quit Visit, blood pressure should be retaken after a 10-minute rest period. If after the second reading the participant still presents with a SBP less than 90 mmHg, the Study Physician will be consulted to determine study eligibility and/or if TN patches should be distributed.

Medical History Form: A medical history form (led by the research staff) will be completed to review for applicable contraindications previously listed under Key Inclusion/Exclusion Criteria at the Intake Visit.

Microbiome Medication Review: Participants who elect to participate in the microbiome sub-study and met the initial microbiome sub-study eligibility criteria at phone screen will be asked about their use of medications that would be considered contraindicated for participation. Those reporting the use of an exclusionary medication will be deemed ineligible to participate in the microbiome sub-study.

fMRI Medical History Form: Participants who are eligible to potentially complete the neuroimaging sub-study and met the initial fMRI eligibility criteria at phone screen will be asked to complete a separate fMRI medical history form to review for applicable contraindications previously listed under Key Inclusion/Exclusion Criteria.

Magnet Safety Form: Participants participating in the neuroimaging sub-study will complete a standard magnet safety form provided by the Department of Radiology at the Hospital of the University of Pennsylvania at the Intake visit and before entering the scanner at each fMRI scan. The magnet safety form assesses a history of specific prosthesis, surgical implants, and a variety of other MRI contraindications.

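### Minor inconsistency in a safety rule: the Pre-Quit mild-hypertension paragraph sets no limit on the other blood pressure component, so 155/104 or 195/95 meets both a release rule and a stricter rule for patches

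*Combined protocol and SAP*

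**What the plan says.** Participants who needed more than one blood pressure reading at Intake are measured again at Pre-Quit. Section 6.2.4, item 4, gives the purpose: they "will complete an additional blood pressure reading to reconfirm eligibility to receive TN as scheduled". If the first Pre-Quit reading is raised, a second is taken after ten minutes' rest. Section 6.5.2 then gives three bullets for the second reading:

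- Pass: SBP "less than 160 mmHg and a DBP less than 100 mmHg, s/he will be ELIGIBLE to receive TN patches as scheduled".
- Letter: for SBP "greater than 159 mmHg and/or DBP greater than 99 mmHg, the participant will be required to obtain written permission" from their physician before patches are given.
- No patches: above 190 mmHg SBP and/or 110 mmHg DBP, the participant is sent for urgent care and may continue counseling, but "they will not have the option to receive TN patches".

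A separate paragraph follows. It covers the first or the second reading and applies "if a participant presents with a SBP between 151-159 mmHg and/or DBP between 91-99 mmHg". Staff tell the participant that the reading may indicate mild, Stage I hypertension and advise seeing a physician. It ends: "The participant will remain eligible for the study and receive TN patches as scheduled".

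The Intake procedures have the same structure. A second reading above 159 and/or 99 makes the person ineligible, while a mild paragraph with the same ranges keeps the person eligible.

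**The concern.** The mild paragraph is triggered by either component alone and ignores the other. The pass bullet, which leads to the same outcome, requires both components to be below the limit. Read literally, the mild paragraph releases patches at readings for which its neighbors demand a letter or withhold patches altogether.

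Pre-Quit is where the first patches are handed out (section 5.5.3), and section 7.1 names uncontrolled high blood pressure among the conditions kept out of the study to limit nicotine risk. Table 2 schedules no blood pressure measurement after Pre-Quit, so a wrong decision here has no planned later check. What is at stake is a dispensing decision for individual participants, not the trial's inference.

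**Working it through.** No published figure is involved. The check applies the rules of section 6.5.2 as logical conditions.

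**Pre-Quit rules, second reading**

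- Pass (P): SBP < 160 and DBP < 100. Patches as planned.
- Letter (L): SBP > 159 or DBP > 99. Patches only after a physician's letter.
- None (N): SBP > 190 or DBP > 110. No patches.
- Mild (M): SBP 151–159 or DBP 91–99. Patches as planned.

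**Readings put through the rules**

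| Reading | Rules met | Result as written |
|---|---|---|
| 155/85 | M (SBP 155), P | Consistent |
| 155/95 | M (both components), P | Consistent |
| 155/104 | M (SBP 155), L (104 − 99 = 5 mmHg over) | Release and letter |
| 195/95 | M (DBP 95), L (195 > 159), N (195 − 190 = 5 mmHg over) | Release, letter and no patches |

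**Extent of the overlap.** Take whole-number readings with SBP 90–220, DBP 50–130 and SBP above DBP. M coincides with L or N in two blocks:

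- SBP 151–159 with DBP 100–130: 9 × 31 = 279.
- DBP 91–99 with SBP 160–220: 9 × 61 = 549.
- Total: 279 + 549 = 828.

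The grid limits are an assumption. The total counts possible pairs of numbers and says nothing about how often they occur.

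**First readings.** M also covers the first reading. A first Pre-Quit reading of 155/104 literally calls for both a repeat measurement and patches as planned.

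**Intake.** A second reading of 155/104 is ineligible because DBP exceeds 99, and eligible because SBP lies in 151–159. A reading of 195/95 conflicts in the same way.

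**Effect of a joint limit.** If M also requires SBP < 160 and DBP < 100, it cannot coincide with L, because for whole-number readings L is exactly the complement of that condition. Since every N reading is also an L reading, M cannot coincide with N either, and the 828 fall to 0. Readings that pass both limits keep their mild-hypertension advice.

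**A second overlap remains.** SBP 195 meets both L, which permits patches once a letter arrives, and N, which does not. Saying that the more severe component governs would not settle this, because one component triggers both bullets. All conflicts at Pre-Quit disappear only if precedence between L and N is also written in.

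**The case against.** The strongest reply is that ordinary reading already resolves the overlap. The three bullets dispose of every second reading. The paragraph after them speaks of mild hypertension and of a participant who remains eligible; that language fits advice for those who have passed, and someone sent for urgent care at 195/95 is plainly not a mild case. Section 4.6 (Medical, item 8) defines uncontrolled hypertension by either component and refers to these procedures. After a missed Pre-Quit visit, "TN patches will not be distributed until the participant presents a blood pressure reading within the established eligibility range". If staff follow the stricter rule wherever two apply, as one must to reconcile the letter and no-patch bullets, every reading has one outcome.

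There are also general safeguards. Section 4.6 (General Exclusion, item 2) says "Subjects may be deemed ineligible for any of the aforementioned reasons at any point throughout the study", and section 10.4 makes the Study Physician's documented approval mandatory before any patches are given.

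Most of this stands as evidence of intent and keeps the point minor. It does not supply the missing rule. No sentence gives precedence for a participant who attends Pre-Quit, and the missed-visit sentence covers a different case. The physician's approval rests on eligibility confirmed after Intake (sections 10.3.2 and 10.4), and nothing requires the Pre-Quit reading to be sent to the physician, although a persistently low SBP does require a consultation. Section 10.3.3 mentions visit checklists and study procedures that may already resolve the matter, but they are not in the documents.

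**Conclusion.** The inconsistency is real and minor. An operative dispensing threshold is worded too broadly in one paragraph at Pre-Quit, and the same gap affects eligibility at Intake.

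A reader might infer that the plan means to give nicotine patches to people with uncontrolled blood pressure, or that some received them wrongly. The documents support neither. The joint limit in the pass bullet, the exclusion criterion, the stated purpose of the Pre-Quit reading and the missed-visit rule all point to the stricter branch, and nothing reports an actual dispensing error.

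The number affected cannot be derived. For a conflict at the second Pre-Quit reading, a participant must have a raised first Intake reading, pass the second, be raised again on the first Pre-Quit reading, and then have a second one that is raised in one component and in the mild band in the other. Few, if any, are likely to meet all four conditions. Both arms follow the same rules, and no endpoint, alpha, power or sample-size figure changes. Confidence is high about the overlap in the text; it does not extend to any consequence in practice.

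**What to change.** 1. In both mild-hypertension paragraphs of section 6.5.2 (Intake and Pre-Quit), add: *provided SBP is below 160 mmHg and DBP is below 100 mmHg*.
2. Either limit the Pre-Quit letter bullet to readings not above 190 mmHg SBP or 110 mmHg DBP, or state that the most restrictive applicable rule governs.
3. Align the visit checklist with the revised text.

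At Pre-Quit, a second reading of 155/104 then needs the physician's letter and 195/95 receives no patches; at Intake both are ineligible. The cost is one clause in each of two paragraphs, one further clause or sentence, and a checklist update. No new measurements are needed and the analysis is unchanged.

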3.1 General Design - Parent (Main) Study

This is a randomized clinical trial of the efficacy of BAS+ plus TN compared to SC plus TN in treatment-seeking smokers. After completing an Intake Visit (~week -3), eligible smokers will be randomized (stratified by nicotine dependence, BMI and gender) to participate in 8 individual sessions of BAS+ or SC over a 10-week treatment period with two sessions prior to the target quit date (weeks -2, -1) and six sessions post-target quit date (TQD [week 0] and weeks 1, 2, 4, 6, and 8). Standard, 8-week; open-label TN will begin on the TQD. Moderators will be assessed pre-treatment. Mediating mechanisms will be assessed before, during, and at the end of treatment (EOT, week 8). Smoking will be assessed by self-report and biochemically confirmed (Carbon Monoxide [CO] < 5 or absence of Urine Cotinine) at all in-center visits (for CO ONLY) after quitting, at EOT (week 8), and at the 12- and 26-week follow-ups. Weight will be assessed at these same time points. Food intake will be measured by three consecutive days of 24-hour food recalls at Baseline [week -2] and 4-, 8-, and 12- and 26-weeks post-TQD. Smoking cessation and PCWG are the primary outcomes and food intake is a secondary outcome at 26-weeks post-TQD. Consistent with intent-to-treat (ITT) analyses, we will measure smoking cessation and weight gain in the full sample at the 26-week follow-up, evaluating a smoking status by treatment interaction for the PCWG analysis.

Time points (i.e. study weeks) displayed in Figure

[figure not shown]
CONFIDENTIAL

This material is the property of the University of Pennsylvania. Do not disclose or use except as authorized in writing by the study sponsor

1 and included within the Study Procedures Section represent approximations. Participants will follow a study schedule similar to that designated in Figure 1 and the Study Procedures, but will be permitted a degree of flexibility based on the maximum/minimum amount of time allowed between each time point established by the Principal Investigator. If a participant is unable to attend an in-person visit within the permissible window of time allotted between time points, counseling and applicable study measures may be completed/collected via telephone. In-person completion of the Intake and Baseline Visits are considered mandatory for study participation.

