4.8 Subject Recruitment

Participants may be recruited from television, radio, internet advertisements, social media, newspaper, flyers, transit posters, referrals, and/or from our database of previous participants who have agreed to be re-contacted for future studies. All advertising materials will be submitted to the UPENN IRB for approval prior to distribution/posting. Interested participants will first complete a telephone screen to assess their initial eligibility. Participants who are initially eligible will be screened against our registration database to confirm that they are not currently participating in another research study at our Center and have not previously reported a condition or circumstance that would make them ineligible for the current study. **If the PI deems it is safe for the participant and research staff, based upon federal and University COVID-19 guidance**, then eligible research participants will be invited to the center to complete an Intake Visit during which they will be presented with the IRB approved Informed Consent Form in-person and have their final eligibility confirmed.

Prior to the Principle Investigator's approval, those participants who remain initially eligible at phone screen will then be invited to review the entire IRB approved Informed Consent Form virtually via REDCap to minimize the participants time spend in the research center during the COVID-19 pandemic. After reviewing the IRB approved Informed Consent Form, the participant will complete a telephone Consent Discussion with a member of the research staff. After the participant has had the opportunity to have their questions answered, signed the consent, and agreed to participate, the participant will complete a Shipley Institute of Living Scale (SILS) virtually via REDCap. Participants whose estimated IQ is 75 according to the WAIS-R conversion based upon the exam will be deemed Ineligible per the Exclusion Criteria above. Participants whose WAIS-R estimated IQ is at least a 75 based upon the Shipley will then be invited to the center to have their final eligibility confirmed at an Intake Visit. Early Withdrawal of Subjects

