Emergency Contact Form: Participants participating in the neuroimaging sub-study form will provide emergency contact information in the event of an emergency at the fMRI scanner.

Demographics, Smoking History, Cigarette Brand, and Nicotine Dependence (FTND): Standard questionnaires will be administered at the Intake Visit to collect the following data: demographics, age at smoking initiation, current smoking rate, previous quit attempts, and own cigarette brand information (Cigarette Brand Form). The Fagerstrom Test for Nicotine Dependence (FTND) will also be administered. The FTND is a 6-item, self-report measure of nicotine dependence derived from the Fagerstrom Tolerance Questionnaire. The FTND scale has satisfactory internal consistency (Cronbach's alpha = .64) and high test-retest reliability ($r=.88$).

ETOH History: An ETOH history questionnaire will be administered at the Intake Visit and will assess alcohol consumption over the past 7 days.

Program Referral Form: Participants who are in contact with current or past study participants may share information exclusive to their assigned counseling condition (BAS+/SC). To avoid this situation and protect blind integrity, participants will be asked to complete a Program Referral Form at the Intake Visit in which they will identify if they know someone currently enrolled or someone who has previously completed the trial. Those acquainted with current or previous participants may be randomized to the same counseling condition (BAS+/SC) at the Principal Investigator's discretion.

Shipley Institute of Living Scale (SILS): All participants will complete the SILS via REDCap prior to coming into the center to complete the remainder of their Intake Visit unless it is deemed safe

CONFIDENTIAL

This material is the property of the University of Pennsylvania. Do not disclose or use except as authorized in writing by the study sponsor

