9.3 Data Processing

The data entry screens will resemble the data collection forms as closely as possible to allow visual referencing during data entry. This data entry module will be configured for single data entry. Participant data will be collected by research staff, recorded on study-specific CRFs, and scanned in or entered directly into the appropriate DMS module. Data entry checks will be included in the entry screen designs where appropriate to limit the opportunity for erroneous entries due to mistyping. Such data entry checks would include value range comparisons, valid data type checks, required value checks, and/or skip pattern enforcement. Following telephone eligibility screening, research staff will perform subject registration. Following the Intake Visit, research staff will randomize eligible subjects. The randomization module will allow the research staff to randomize subjects into one of the two trial arms. At the randomization attempt, the DMS will check the eligibility data to confirm that randomization is valid. A randomization assignment will then be provided.

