10.2 Staff Training

Staff training will consist of an initial explanation and review of the protocol, informed consent form, CRFs and laboratory tasks, sample collection protocols, data management system, adverse event collection and reporting, and all study-specific SOPs. In addition, during a standardized training period, the duties of each staff member will be clearly outlined and all applicable regulations will be reviewed. The Principal Investigator, [name], will oversee the behavioral activation intervention and smoking cessation counseling training, as well as the transdermal nicotine procedures. Training interactions will be documented in a training log, which will be maintained within the regulatory binder. Senior personnel will supervise junior staff and provide re-training as needed.

[name] and senior staff will oversee the development of protocols for activities pertaining to the neuroimaging sub-study and training of staff in these protocols. [name] and/or the Project Manager will also be responsible for the development of procedures pertaining to all

CONFIDENTIAL

This material is the property of the University of Pennsylvania. Do not disclose or use except as authorized in writing by the study sponsor

neuroimaging study visits and implementing and monitoring ongoing staff training procedures accordingly.

All personnel working on this project will complete required training in the protection of human subjects and the protection of personal identifiable information (i.e. HIPAA) before interacting with study data or research participants. All human subject and privacy protections certifications will be maintained in the regulatory binder.

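### Acquaintances of participants may be placed in the same arm at the Principal Investigator's discretion, so some may not be independently randomised, and the analysis plan makes no provision for this

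*Combined protocol and SAP*

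**What the plan says.** Section 6.5.2 is concerned that people who know each other may share material specific to one counselling condition. It gives the purpose of the form as follows: "To avoid this situation and protect blind integrity, participants will be asked to complete a Program Referral Form at the Intake Visit". On that form "they will identify if they know someone currently enrolled or someone who has previously completed the trial". The consequence is that people with such an acquaintance "may be randomized to the same counseling condition (BAS+/SC) at the Principal Investigator's discretion". The section gives no criterion for using the discretion, no cap, and no rule for someone who knows participants in both arms. It does not mention recording who was placed.

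The other descriptions of allocation contain no such exception. Section 3.1 says "eligible smokers will be randomized (stratified by nicotine dependence, BMI and gender". Section 9.3 says "The randomization module will allow the research staff to randomize subjects into one of the two trial arms", after the Intake Visit and a check of eligibility, and the system then returns an assignment. No override is described.

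Section 6.10 fits GEE models to the full sample with treatment assignment, time point, adherence and covariates. It has no term for placed participants, no clustering of linked people, and no sensitivity analysis for them. Section 6.7 makes no allowance for them in the sample size.

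Acquaintances are a plausible group, because section 4.8 lists these recruitment sources: "flyers, transit posters, referrals, and/or from our database of previous participants".

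**The concern.** Section 6.5.2 uses the word randomised, but a person who must join an acquaintance's arm is not randomised. That arm follows from an earlier assignment and from a case-by-case decision on whether to apply the rule. Three problems could follow.

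- **Concealment.** The form is completed at Intake and allocation comes afterwards. For an acquaintance, the likely arm could be known to anyone who knows the earlier participant's arm. A discretionary decision made with that knowledge is the route to selection bias that concealed randomisation is meant to close.
- **Entry that depends on treatment.** Whom a participant refers may depend on the counselling received. Placing the referred person in the same arm would turn that into a baseline difference between arms.
- **Dependence.** Linked people in the same arm may have correlated outcomes, while the models treat participants as independent of one another.

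At stake is whether the primary comparisons at week 26 rest wholly on randomisation, and whether the trial could show that they do.

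**Working it through.** **Inputs from the documents.** Section 6.7: 13% abstinent on SC and 25% on BAS+, 213 per arm, 0.025 per primary outcome, 82% power. Section 4.2: about 340 randomised and followed to week 26, taken here as 170 per arm. The number placed, their quit rate, their split between arms and their correlation with acquaintances are not in the documents. All are assumed below.

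**1. The plan's own power.** For the pooled two-sided z-test with z = 2.2414 (0.025 two-sided):
- Standard error under no difference: √(2 × 0.19 × 0.81 / 213) = 0.0380
- Standard error under the alternative: √((0.13 × 0.87 + 0.25 × 0.75) / 213) = 0.0376
- (0.12 − 2.2414 × 0.0380) / 0.0376 = 0.926, so power is 82.3%

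The log odds ratio version gives 80.8%. The stated 82% reproduces and is not in dispute.

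**2. Bias in the abstinence difference.** Let k people be placed, a share s of them in BAS+, with a quit rate d points above the others. With 170 per arm:

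bias = k × (2s − 1) × d / 170

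With d = 15 points:

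| Placed | 60/40 split | 75/25 split | All in BAS+ |
|---|---|---|---|
| 7 (2%) | 0.12 | 0.31 | 0.62 |
| 17 (5%) | 0.30 | 0.75 | 1.5 |
| 34 (10%) | 0.60 | 1.5 | 3.0 |

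For example, 17 × 0.2 × 15 / 170 = 0.30. Against the planned 12-point difference, the 5% row is 2.5%, 6.25% and 12.5% of the effect. The standard error of the difference at 170 per arm is √(0.3006 / 170) = 4.2 points, so 0.3 to 0.75 points is about 0.07 to 0.18 of a standard error. The sign reverses if placement favours SC.

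**3. Type I error from selective placement.** This check takes 426 in total and no true effect, with 13% quitting among randomised people, 20% to 25% among placed people, and 60% to 75% of the placed in BAS+.
- 5% placed: bias 0.1 to 0.6 points, type I error 0.025 to 0.027
- 10% placed: bias 0.25 to 1.1 points, type I error 0.025 to 0.033
- 20% placed: bias 0.45 to 1.9 points, type I error 0.026 to 0.048

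**4. Ignored dependence.** If each placed person forms a pair with one earlier participant, the design effect is about 1 + 2f × ICC, where f is the share placed. At f = 5% and ICC 0.05 to 0.30 it is 1.005 to 1.03. Standard errors are then understated by at most about 1.5% (√1.03 = 1.015), and the type I error is 0.0254 to 0.0272. At f = 20% and ICC 0.30 it is 1.12, with type I error 0.034.

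**5. Power if placed people are excluded.** The formula in step 1 with 213 × (1 − f) per arm gives:
- f = 5%, 202.35 per arm: 80.1%
- f = 10%, 191.7 per arm: 77.7%

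Starting from 170 per arm, the same test has 72.1% power with nobody excluded, 69.6% at f = 5% and 67.0% at f = 10%.

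**The case against.** The strongest defence is that the rule has a legitimate purpose and may rarely be used. Contamination between counselling conditions would dilute the comparison, and section 6.5.2 says openly that the rule is there to limit it. The wording is permissive. At a share of about 5% with a mixed split, the effect on both bias and standard errors is small. All of this stands, and it limits the size of the point. It does not justify discretion, because a fixed rule that sends every acquaintance to the same arm limits contamination at least as well.

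Three stronger readings are tempting, and the documents do not support them.

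- **The investigator assigns people knowing the arm.** No section says that the investigator knows the earlier participant's arm when deciding. Section 10.2 says that the investigator "will oversee the behavioral activation intervention and smoking cessation counseling training", which covers both conditions and shows no one-sided interest. Section 9.7.1 has the investigator review audio recordings for training. That makes knowledge of arms plausible but does not place it at the time of allocation.
- **These people are unmarked.** Everyone completes the Program Referral Form at Intake, so acquaintance is recorded before allocation. What is missing is a described record of who was actually placed, and any planned use of it.
- **They should be dropped from the primary analysis.** That would depart from the full-sample intention-to-treat plan in section 6.10 and cost power in the main test. If a fixed rule applied to every acquaintance, allocation would resemble randomisation of small clusters, and the case for dropping them would be weaker still.

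**Conclusion.** The point holds in a limited form. A stated rule allows some participants to be allocated without independent randomisation. Sections 3.1 and 9.3 do not acknowledge it, and section 6.10 would analyse such people as if they had been randomised.

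A reader might infer that part of the sample was in fact not randomised, or that the treatment effect is inflated by an eighth. Neither follows. The number placed is unknown and may be zero, and the 1.5-point figure (an eighth of 12) needs all 17 assumed people to be in BAS+. With 5% placed and an assumed 15-point advantage, 0.3 to 0.75 points is the range for a mixed split, and the understatement of standard errors is minor. The effect would become material only with a much larger share placed, unequal prognosis and an uneven split together. As the plan stands, the trial could not show which case applied.

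**What to change.** 1. **Section 6.5.2:** remove the discretion. State one rule for every acquaintance declared on the Program Referral Form, for example always the arm of the earliest-enrolled named acquaintance, or always independent randomisation. The first form also settles the case of someone who knows participants in both arms.
2. **Sections 3.1 and 9.3:** describe the rule as part of allocation and have the randomisation module apply it. Store a flag for anyone not independently randomised and an identifier for the linked group, and report the flagged participants by arm.
3. **Section 6.10:** keep all participants in the primary intention-to-treat analysis. Use robust standard errors clustered on the linked group, with an unlinked participant as a cluster of one. Prespecify a sensitivity analysis that excludes placed participants.

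If allocation is already complete, the forms still identify acquaintances. Where it cannot be established who was placed, the sensitivity analysis can exclude everyone who declared an acquaintance.

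The cost is protocol and SAP wording, a flag and a group identifier, and slightly wider standard errors. Only the sensitivity analysis loses sample: on the section 6.7 inputs its power is about 80% at 5% placed and 78% at 10%, against 82%. No new data collection is needed, since the form already asks the question before allocation. If independent randomisation is chosen as the rule, some contamination between acquaintances has to be accepted.
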